7.1.4. Laboratory Assessments

The laboratory must provide normal reference ranges for all hematology, chemistry, coagulation tests, and urinalysis/urine parameters shown in [Table 12](#). Laboratory results for hematology, serum chemistry, coagulation and urine assessments must be reviewed for clinically significant events. Any clinically significant events must be followed and reported as required by the protocol (see [Section 10](#)). Laboratory assessment prior to the first day of dosing may be done up to 72 hours prior to dosing.

7.1.5. Ophthalmological Assessments

Ophthalmological examination will be performed by an ophthalmologist or qualified person at the time points described in [Section 1.3](#).

Ophthalmologic exam should be performed for each eye and should encompass:

- Best corrected visual acuity
- External ocular examination
- Routine slit lamp examinations, including the anterior and posterior chambers (Fluorescein or rose Bengal or other dyes used to evaluate the ocular surface can be used according to institutional guidelines and local clinical practice)

Any clinically significant findings must be reported as an AE. The type of examination used to identify any potential ocular adverse event AEs will be captured in the electronic case report form (eCRF).

7.1.6. PRO Measurements

For patients enrolled in Part C, patients' health-related quality of life, symptoms, functioning, and general well-being will be captured using PRO measures and collected according to the Schedule of Events (Section 1.3).

EORTC-QLQ-C30:

The EORTC-QLQ-C30 consists of 30 core items, with the 4-point Likert scales ranging from 1: "Not at all" to 4: "Very much". There are 2 items for global health status/quality of life. Functional scales include physical functioning (5 items), role functioning (2 items), emotional functioning (4 items), cognitive functioning (2 items), and social functioning (2 items). Symptom scales/items include fatigue (3 items), nausea and vomiting (2 items), pain (2 items), dyspnea; insomnia; appetite loss; constipation; diarrhea; and financial impact (1 item each).^{30,31}

EQ-5D-5L:

The EuroQol-5D (EQ-5D) is a standardized measure of the patient's health-related quality of life. The 5-level version of the EQ-5D (EQ-5D-5L) consists of 2 pages: the EQ-5D descriptive system and the EQ visual analogue scale (EQ VAS). The EQ-5D-5L descriptive system comprises the following five dimensions: mobility, self-care, usual activities, pain/discomfort and anxiety/depression. Each dimension has 5 levels: no problems, slight problems, moderate problems, severe problems, and extreme problems. The EQ VAS records the patient's self-rated health on a vertical visual analogue scale where the endpoints are labelled 'The best health you can imagine' and 'The worst health you can imagine'. The VAS can be used as a quantitative measure of health outcome that reflects the patient's own judgement. See <https://euroqol.org/eq-5d-instruments/>.

7.1.7. COVID-19 Pandemic Considerations

- During the COVID-19 pandemic, the Sponsor will perform a risk assessment of the study on an ongoing basis to ensure:
- The protection of patient safety, particularly if scheduled visits to the sites are postponed
- The uninterrupted supply of drugs to patients for whom the drugs continue to benefit, while assuring patient safety (even if they are forced to remain at home)
- The collection of key safety and efficacy data even if patients cannot keep their scheduled visits to the site due to the exceptional circumstances in relation to COVID-19

The following considerations may be applied in accordance with guidelines from regulatory authorities^{17,18} and individual site policies:

- If a patient is unable to sign an informed consent for the study in person, the consent may be obtained electronically or remotely via a phone call or video conference.
- If a patient is unable to attend a scheduled on-site visit and/or complete any protocol-required study assessments, the Sponsor should be contacted. Clinical assessments should be performed remotely via a phone call or video conference, assuring safety assessment and collection of new/follow-up AEs.

- To ensure compliance with the protocol-required laboratory tests and assessments, the possibility for these tests to be performed at an external qualified laboratory or facility should be evaluated. The results of any tests or assessments performed by an external laboratory or facility must be communicated to the Investigator and documented in the patient's source files. If it is not possible to have assessments performed at an external facility, the patient may be evaluated for safety via a phone call or video call, assuring the collection and follow-up of AEs are documented in the patient's source file.
- Tumor assessments should be performed (as much as the circumstances allow) as specified in the protocol. If a patient is unable to reach the site, an external qualified imaging facility can be used. Every effort should be made to ensure that the same imaging modality and image acquisition parameters (eg, anatomic coverage, imaging sequences, etc.) are used consistently for each patient throughout the study.
- The results (including the images obtained from all radiographic procedures) should be sent to the Investigator. The imaging facility used, the time points, and the Investigator's review of the images should be documented in the patient's source files and the eCRF.
- If a patient becomes infected with severe acute respiratory syndrome coronavirus 2 (SARS-CoV-2) and/or develops any symptoms suggesting COVID-19 infection, Investigators must follow local guidelines for the management of patients with COVID-19. Symptomatic COVID-19 cases should be reported as AEs or SAEs; however, asymptomatic COVID-19 cases do not have to be reported. The Sponsor needs to be contacted to discuss the continuation of the study treatment. However, the Investigator has the right to decide the continuation of treatment in COVID-19 infected patients.
- Considering the rarity of the disease (even after the COVID-19 pandemic settlement), the remote management options described above may apply to patients who are unable to frequently visit the sites for any other reasons (eg, extremely long distance to the sites) after discussion with the Sponsor.
- All decisions and deviations due to COVID-19 must be documented in the patient's source files and the eCRF.

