Other Nonhematologic	
 • Any other Grade ≥3 toxicities with the following exceptions: 
 – Grade 3 nausea, vomiting, and diarrhea lasting <72 hours despite optimal supportive care. Grade 4 vomiting or diarrhea will be considered a DLT. – Fatigue lasting <7 days – Asymptomatic Grade 3 electrolyte abnormality with a duration of ≤72 hours that can be substituted or treated and are clinically uncomplicated (eg, not requiring hospitalization). – Grade 3 amylase or lipase elevation not associated with symptoms or clinical manifestations of pancreatitis

Toxicity	DLT Definition
Other	
 • Prolonged dose interruption (>2 weeks) in initiating Cycle 2 due to study drug-related toxicity) • Any study drug related AE(s) leading to treatment discontinuation during Cycle 1 despite optimal supportive treatment • Any death not clearly due to the underlying disease or extraneous causes. • Any other toxicity deemed a DLT and agreed upon between Sponsor and Investigator

Abbreviations: AE=adverse event; ALP=alkaline phosphatase; ALT=alanine aminotransferase; ANC=absolute neutrophil count; AST=aspartate aminotransferase; DLT=dose-limiting toxicity; ULN=upper limit of normal

A patient evaluable for DLT is defined as a patient who either experienced a DLT during the first cycle (including the PK Lead-in period for patients in Part A1), or who completed the first cycle without experiencing a DLT and with at least 80% of study treatment administered. Patients who are not evaluable for DLTs may be replaced. Trends for toxicities observed after the DLT period will be considered when selecting the RP2D.

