12.5. Analysis Populations

The analysis populations in the study are defined in [Table 17](#).

Table 17: Definitions of Analysis Populations

Analysis Population	Definition
All Consenting Population	All patients who signed the ICF.
All Treated Population	All patients who received at least one dose of the study drug. This is the primary population for dosing, efficacy, and safety analyses.
DLT Evaluable Population	All patients in the Dose Escalation, except backfill patients, who either experienced a DLT during the 1st cycle of treatment including PK lead-in period, or who completed the 1st cycle without experiencing a DLT and with at least 80% of planned study treatments administered. This is the specific population for DLT summarization.
PK Analysis Population	All patients who received at least one dose of study drug and have at least one post-dose TAS3351 and/or TAS-05-14317 plasma concentration measurement will be evaluated for PK; unless significant protocol deviations may have affected the data or if key dosing information is missing. This is the primary population for PK analysis.
Pharmacodynamic/Biomarker Analysis Population	All patients in the All-Treated Population who have at least one evaluable baseline and one evaluable post-dose pharmacodynamic/biomarker data point for analyses.

Abbreviations: DLT=dose-limiting toxicity; ECG=electrocardiogram; PK=pharmacokinetic

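### A Part A1 patient whose Cycle 1 laboratory tests or ECGs were missed still counts as DLT-free in BOIN, because DLT evaluability requires no tests and Section 7.1.7 allows remote safety evaluation in the DLT window

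*Protocol*

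**What the plan says.** Protocol Section 7.1.7 sets out an order of steps for a patient who cannot attend. The Sponsor is contacted. For laboratory tests and other assessments, "the possibility for these tests to be performed at an external qualified laboratory or facility should be evaluated". Only then comes the fallback: "If it is not possible to have assessments performed at an external facility, the patient may be evaluated for safety via a phone call"; contact by video is accepted as well. A later bullet carries these options beyond the pandemic: "the remote management options described above may apply to patients who are unable to frequently visit the sites for any other reasons", with long distance as the example and again after discussion with the Sponsor. The section names no study part or cycle to which this does not apply.

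Protocol Section 6.1.2 counts as evaluable a patient with a DLT in the first cycle, or one "who completed the first cycle without experiencing a DLT and with at least 80% of study treatment administered". Table 17 and SAP Table 3 define the DLT Evaluable Population the same way: "completed the 1st cycle without experiencing a DLT and with at least 80% of planned study treatments administered". None of the three places mentions a laboratory test or an ECG. Section 6.1.2 allows non-evaluable patients to be replaced, but missing tests do not make a patient non-evaluable.

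Tests are scheduled. Protocol Table 1 has hematology and chemistry on Day -3 (PK lead-in) and on Days 1, 8 and 15 of Cycle 1, then on Day 1 of Cycle 2 (C2D1). Section 6.1 requires on-site dosing on PK days.

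**The concern.** The BOIN rule acts on the number of patients with a DLT among those evaluable. A patient can be DLT-free because the tests were done and showed nothing, or because they were not done. The definition treats the two alike.

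The difference matters for the DLTs listed in Table 7. Every hematologic, hepatic and renal entry needs a laboratory value; even febrile neutropenia needs a neutrophil count. Some need serial values: Grade 4 neutropenia beyond 7 days, creatinine clearance below 30 mL/min beyond 3 days, and the 7-day transaminase criterion for patients with liver metastases. QT prolongation is not named in Table 7, but at Grade 3 or higher it falls under the residual non-hematologic category and needs an ECG. The protocol anticipates liver, hematologic and QT effects (Sections 2.2.1.4 to 2.2.1.6) and relies on laboratory tests and ECGs to monitor them.

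At stake is the DLT incidence, a primary endpoint of Part A, and the escalation decisions taken on it in a first-in-human study. The 30% enrollment stop for Parts A2 and B in Section 4.2.4 also counts Cycle 1 events meeting the DLT definition, and it states no assessment requirement for its denominator.

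**Working it through.** **1. The plan's own BOIN figures.** Inputs from Protocol 12.7.4.1: Φ = 0.30, Φ1 = 0.6 × 0.30 = 0.18, Φ2 = 1.4 × 0.30 = 0.42.

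- λ1 = ln[(1−Φ1)/(1−Φ)] / ln[Φ(1−Φ1)/(Φ1(1−Φ))] = ln(0.82/0.70) / ln(0.246/0.126) = 0.2365
- λ2 = ln[(1−Φ)/(1−Φ2)] / ln[Φ2(1−Φ)/(Φ(1−Φ2))] = ln(0.70/0.58) / ln(0.294/0.174) = 0.3585

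These match the stated 0.236 and 0.359. Taking floor(nλ1) and ceiling(nλ2) reproduces the escalate and de-escalate rows of Table 6 for n = 1 to 15. The elimination row is reproduced with a Beta(1,1) prior (an assumption) and the 95% overdose rule. The BOIN figures contain no error.

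**2. What one unseen DLT does.** At n = 3, floor(0.709) = 0 and ceiling(1.076) = 2. So 0 DLTs means escalate, 1 means stay and 2 means de-escalate. One missed DLT turns stay into escalate, or de-escalate into stay.

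**3. Where the gap is open** (Protocol Tables 1, 13 and 14):

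| Part | On-site PK/ECG days in or closing Cycle 1 | Scheduled laboratory visits with no PK day |
|---|---|---|
| A1, QD | Day -3 to 72 h, C1D15, C2D1 | Day 8 |
| A1, BID | C1D1, C1D15, C2D1 | Day 8 |
| A2 and B | C1D1, C2D1 | Day 8, Day 15 |

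Footnote a of Tables 13 and 14 lets PK days be postponed or waived after a dose interruption with written Sponsor approval, and lets time points be skipped on written notification when no longer needed for PK.

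**4. Illustrative size.** The documents give neither the number of untested patients, u, nor the share of DLTs visible only by laboratory test or ECG, f. Both are assumptions. With true DLT rate p:

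P(0/3) = (1−p)^(3−u) × [1 − p(1−f)]^u

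| p | u = 0 | u = 1, f = 0.3 | u = 1, f = 0.5 | u = 1, f = 0.7 |
|---|---|---|---|---|
| 0.42 | 0.58³ = 0.195 | 0.3364 × 0.706 = 0.237 | 0.3364 × 0.790 = 0.266 | 0.3364 × 0.874 = 0.294 |
| 0.30 | 0.70³ = 0.343 | 0.49 × 0.79 = 0.387 | 0.49 × 0.85 = 0.4165 | 0.49 × 0.91 = 0.446 |

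The expected observed rate with one of three untested is p(1 − f/3). At p = 0.42 this is 0.378, 0.350 and 0.322 for f = 0.3, 0.5 and 0.7. The middle value already lies below the de-escalation boundary of 0.359.

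The effect is diluted in larger groups. With one untested patient of six and f = 0.5, the probability of escalating goes from 0.203 to 0.253 at p = 0.42, and from 0.420 to 0.474 at p = 0.30.

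Here an untested patient has no DLT-detecting test in the whole of Cycle 1. If only Day 8 is missed, the relevant share is smaller: the DLTs that Day 8 would have shown and that C1D15 and C2D1 do not.

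**The case against.** The strongest reply is that the schedule already brings Part A1 patients to the site. Day 15 is a full PK and ECG day, C2D1 has a pre-dose PK sample and an ECG, and QD patients also have the lead-in. A patient who keeps those visits is tested at least twice after continuous dosing begins, even if Day 8 is done by phone. Phone-only evaluation is a last resort after Sponsor contact and the search for an external facility, and Section 10.2 separately permits external laboratories. Escalation calls and safety meetings (Section 6.1.2) give people a chance to notice missing data, and the RP2D rests on the totality of data.

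Most of this stands as a limit on how often the gap arises and how wide it is. It does not say how a patient with missing tests is counted, and the written rule counts that patient as DLT-free.

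A reader might infer that any patient who cannot travel may be followed by phone, and that laboratory and ECG toxicities could then not have been seen. The documents do not support that. The Sponsor and external-facility steps come first, and the on-site days remain in the Part A1 schedule. A reader might also extend the formula to a cohort with all three patients untested (0.79³ = 0.493 at p = 0.42, f = 0.5); nothing in the documents makes that plausible.

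Nor should every laboratory abnormality be added to the list. Table 7 excepts asymptomatic, uncomplicated Grade 3 electrolyte changes of up to 72 hours, and Grade 3 amylase or lipase elevation without signs of pancreatitis. Section 2.2.1.11 describes class toxicities as typically gastrointestinal, dermatologic and ocular, many of them visible without a test, which argues against a high f.

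**Conclusion.** The concern holds in a limited form. Section 7.1.7 does not exclude the Part A1 DLT window, and no definition of DLT evaluability in either document requires the tests by which several DLTs are recognized. A patient without them is counted as DLT-free. In Part A1 the exposure is mainly Day 8 and any waived or missed PK visit. In Parts A2 and B it is wider, because no PK day falls between C1D1 and C2D1.

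The direction is certain: a missed DLT can only lower the observed rate. The size is not known. The increase in P(0/3) at a true rate of 0.42, from 19.5% to between 23.7% and 29.4%, assumes one of three patients wholly without DLT-detecting tests and f between 0.3 and 0.7, neither of which the documents give. If remote-only follow-up in Cycle 1 is rare, the practical effect is small. The gap is still worth closing, because the tests are already scheduled and the change is short.

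**What to change.** In Protocol 6.1.2, Table 17 and SAP Table 3, state that a patient without a DLT is evaluable only if a minimum set of the scheduled Cycle 1 tests was obtained:

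- hematology and chemistry from a stated minimum of the Day 8, Day 15 and C2D1 pre-dose visits, within window, at the site or an external laboratory;
- in Part A1, at least one on-treatment Cycle 1 ECG, for example on C1D15.

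A patient without a DLT who lacks this minimum is non-evaluable and may be replaced. A patient with a DLT stays evaluable whatever was missed. Requiring every Cycle 1 ECG would be too strict, since Tables 13 and 14 let time points be skipped. The closing laboratory visit should be C2D1 pre-dose, because Table 1 has no separate end-of-cycle visit.

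Add a cross-reference from Section 7.1.7 saying how remote management in the DLT window affects evaluability. Apply the same condition to the denominator of the 30% rule in Section 4.2.4: the DLT Evaluable Population is confined to Dose Escalation and excludes backfill patients, so amending its definition alone does not reach Parts A2 and B.

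The cost is a few sentences and an occasional replacement patient in Part A1. No new assessment is needed.

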8. PHARMACOKINETICS

8.1. Sample Collection

Blood samples for PK analysis and ECG sampling will be collected at specific time points listed in Table 13 (Table 14 in case BID dosing will be explored) and used to evaluate PK of TAS3351 and its active metabolite (TAS-05-14317). ECGs should also be obtained prior to on-site TAS3351 administration. When a 12-lead ECG is obtained at the same timepoint as a PK blood draw, the 12-lead ECG should be obtained first.

Detailed information about collection procedures including blood sampling, collection, processing, and sample shipment will be provided in a separate Laboratory Manual.

Table 13: Schedule for PK and ECG Sampling (QD Dosing)

Phase 1 Dose Escalation (Part A1)			
Day of Study ^a	Collection time relative to TAS3351 administration (time window ^b)	PK sample	ECG ^c
PK Lead-in, Day -3	Pre-dose (up to -30 minutes)		X
	0.5 hours (±10 minutes)	X	
	1 hour (±10 minutes)	X	X
	2 hours (±15 minutes)	X	X
	3 hours (±20 minutes)	X	
	4 hours (±25 minutes)	X	X
	6 hours (±35 minutes)	X	
	8 hours (±45 minutes ^d)	X	X
	24 hours (±2 hours)	X	X
	48 hours (±2 hours)	X	
	72 hours (± 2 hours ^e)	X	X
Cycle 1 Day 15	Pre-dose (up to -30 minutes)	X	X
	0.5 hours (±10 minutes)	X	
	1 hour (±10 minutes)	X	X
	2 hours (±15 minutes)	X	X
	3 hours (±20 minutes)	X	
	4 hours (±25 minutes)	X	X
	6 hours (±35 minutes)	X	
	8 hours (±45 minutes ^d)	X	X
	24 hours (±2 hours ^e)	X	X
Cycle 2 Day 1	Pre-dose (up to -30 minutes)	X	X (Local)
Cycle 3 Day 1	Pre-dose (up to -30 minutes)	X	X (Local)

Phase 1 “Backfill” (Part A2), Dose Expansion (Part B), and Phase 2 (Part C)			
Day of Study^a	Collection time relative to TAS3351 administration (time window^b)	PK sample	ECG^c
Cycle 1 Day 1	Pre-dose (up to -30 minutes)	X	X (Local)
	2 hours (±1 hour)	X	X (Local)
Cycle 2 Day 1	Pre-dose (up to -30 minutes)	X	X (Local)
	2 hours (±1 hour)	X	X (Local)
Cycle 3 Day 1	Pre-dose (up to -30 minutes)	X	X (Local)

^a For patients with TAS3351 dose interruptions, PK days might be postponed or waived upon discussion and written approval by the Sponsor. Additional optional PK samples may be collected if any safety concerns are identified. If no longer needed for PK evaluation, collection time points might be skipped upon written notification by the Sponsor.

^b Time window given for guidance; collection outside these windows will not be considered a protocol deviation as long as the exact time of dosing and sampling is documented.

^c ECG must be collected prior to PK sampling. All ECGs through C3 should be performed in triplicate. Central ECGs will be performed for all timepoints unless otherwise specified.

^d This PK sample is mandatory for Dose Level 1. Following PK analysis for Dose Level 1, PK sampling at this timepoint at subsequent dose levels may be waived by the Sponsor, with this decision to be communicated to sites.

^e This PK sample must be collected prior to TAS3351 administration on this day. The ECG should be performed within 30 min prior to C1D1 dosing.

Table 14: Schedule for PK and ECG Sampling (BID Dosing)

Phase 1 Dose Escalation (Part A1)			
Day of Study^a	Collection time relative to TAS3351 administration (time window^b)	PK sample	ECG^c
Cycle 1 Day 1	Pre-dose (up to -30 minutes)		X
	0.5 hours (±10 minutes)	X	
	1 hour (±10 minutes)	X	X
	2 hours (±15 minutes)	X	X
	3 hours (±20 minutes)	X	
	4 hours (±25 minutes)	X	X
	6 hours (±35 minutes ^d)	X	
	8 hours (±45 minutes ^e)	X	X
	24 hours (±2 hours ^f)	X	
Cycle 1 Day 15	Pre-dose (up to -30 minutes)	X	X
	0.5 hours (±10 minutes)	X	
	1 hour (±10 minutes)	X	X
	2 hours (±15 minutes)	X	X
	3 hours (±20 minutes)	X	

Phase 1 Dose Escalation (Part A1)			
	4 hours (± 25 minutes)	X	X
	6 hours (± 35 minutes ^d)	X	
	8 hours (± 45 minutes ^e)	X	X
	24 hours (± 2 hours ^f)	X	
Cycle 2 Day 1	Pre-dose (up to -30 minutes)	X	X (Local)
Cycle 3 Day 1	Pre-dose (up to -30 minutes)	X	X (Local)

^a For patients with TAS3351 dose interruptions, PK days might be postponed or waived upon discussion and written approval by the Sponsor. Additional optional PK samples may be collected if any safety concerns are identified. If no longer needed for PK evaluation, collection time points might be skipped upon written notification by the Sponsor.

^b Time window given for guidance; collection outside these windows will not be considered a protocol deviation as long as the exact time of dosing and sampling is documented.

^c ECG must be collected prior to PK sampling. All ECGs through C3 should be performed in triplicate. Central ECGs will be performed for all timepoints unless otherwise specified.

^d Following PK analysis for Dose Level 1 (QD dosing), PK sampling at this timepoint may be waived by the Sponsor, with this communication to be communicated to sites.

^e This PK sample must be collected prior to administration of the second BID dose.

^f This PK sample must be collected prior to administration of the first BID dose on next study day.

Note: For patients enrolled in Phase 1 “Backfill” cohorts (Part A2), Dose Expansion (Part B), or Phase 2 (Part C), PK and ECG sample collection will follow the same schedule outlined in [Table 13](#).

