6.1.1. Dose Escalation

The starting dose of TAS3351 will be 50 mg QD (Table 5). The study is designed to escalate TAS3351 up to a dose of 700 mg daily based on safety and tolerability observed, with lower increments considered, if clinically relevant toxicities are observed. The upper end of 700 mg TAS3351 total daily dose levels are based on more conservative assumptions for PK predictions and non-clinical efficacy data observed. In case of toxicity, other dose levels, such as intermediate or dose levels lower than Dose Level 1, may be explored following discussion and agreement between the Sponsor and the Investigators.

Table 5: TAS3351 Dose Levels

Dose Level	Total Daily Dose (mg/d)	Absolute and % Change from Previous Total Daily Dose
-1	25	-25 mg / -50%
1 (Starting dose)	50	-
2	100	50 mg / 100%
3	200	100 mg / 100%
4	350	150 mg / 75%
5	500	150 mg / 43%
6	700	200 mg / 40%

Note: If no DLTs observed at 700 mg QD, any further dose escalation will not exceed 33% increments.

In addition, if PK, pharmacodynamic, and/or safety data indicate that splitting the dose of TAS3351 in two daily doses might be preferable (eg, due to short half-life, saturation of exposure), then twice daily (BID) dosing of TAS3351 may be explored following discussion and agreement between the Investigators and the Sponsor. In such case, the dose of the highest QD dose shown previously to be safe and tolerable will be divided into two equal doses to be taken in the morning and evening approximately 12 hours apart. Dose escalation for twice daily dosing will follow total daily doses shown in Table 5 (ie, total daily dose divided by 2 for BID dosing).

The planned dose escalation will follow a BOIN design, [REDACTED]. For further information about statistical considerations, please see Section 12.

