5.6.7. Time-Matched QTcF versus Plasma Concentration Analysis

Change from baseline QTcF (Δ QTcF) versus time-matched plasma concentration will be plotted for PK Lead-in Day -3 (for QD dosing) or Day 1 (for BID dosing if applicable) and Day 15 (for both QD dosing and BID dosing, if applicable) of Cycle 1 for PK/ECG Analysis Population in the Dose Escalation portion of the study. In addition, the relationship between plasma concentration of TAS3351 and Δ QTcF will be modeled using a linear mixed-effects model where Δ QTcF is the dependent variable, plasma concentration, nominal day (categorical), nominal time post-dose (categorical), and influence of baseline on intercept are independent

variables, and with random effect of patient on the intercept and slope under an unstructured covariance matrix. In case of convergence or estimation issues, model may be fit without random effect for concentration on the slope and/or intercept. Age, sex and body-weight may be included as a covariate. Additional covariates may be explored to be included in the model. Covariates will be added one at a time to the base model described above and compared using Akaike Information Criterion (AIC). If AIC of the model with covariate is less than that of the AIC of base model and p-value for covariate is less than 0.05 then the covariate will be retained in model. The relationship between plasma concentration of active metabolite TAS-05-14317 and Δ QTcF will be modeled using a similar mixed model as parent. Any interaction between TAS3351 and TAS-05-14317 may also be characterized. Note that for QTcF measurements collected in triplicate at nominal timepoints, the mean of the triplicate measurements will be used in the analysis.

The following will be presented in tabular form for TAS3351 and TAS-05-14317 separately:

- Slope of plasma concentration effect on Δ QTcF
- Standard error of plasma concentration effect on Δ QTcF
- P-value of slope of plasma concentration effect
- P-value of overall model fit (from the likelihood ratio test)

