In addition, the predicted mean change from baseline QTcF (in milliseconds) will be presented for each dose level using the same linear mixed-effects models as described above, where plasma concentration is specified as the geometric mean C_{\max} for each dose level on a specific visit. The predicted mean change from baseline QTcF (in milliseconds) may also be presented for each dose level using the same linear mixed-effects models as described above, where plasma concentration is specified as the maximal observed concentration at each dose level. A double-sided 90% confidence interval for the predicted mean Δ QTcF will also be presented.

The following model assumptions will be evaluated by the indicated exploratory plots:

- Assumption 1: No drug effect on HR
 - Time course of mean Δ HR effects by dose will be plotted
- Assumption 2: QTcF interval is independent of HR
 - QTcF vs RR will be plotted
 - The adequacy of the correction formula will be assessed by determining the linear relationship of QTcF to RR. Adequacy will be evaluated based on the population QTcF:RR slope. If QTcF is determined to be an inadequate correction, then another fixed-formula rate correction may replace the primary endpoint of QTcF
- Assumption 3: No time delay between drug concentrations and Δ QTcF
 - Time course of mean concentrations and mean Δ QTcF by dose will be plotted
- Assumption 4: Linear C-QTcF relationship
 - Δ QTcF versus concentration will be plotted with a trend line included

If significant hysteresis is found, another model (e.g., Emax model, effect-compartment model) should be explored.

Goodness-of-fit plots, including but not limited to Model predicted vs observed $\Delta Q T c F$, Quartile-Quartile plot of residuals, Concentrations vs residuals, Baseline $Q T c F$ vs residuals, Time vs residuals, and Quantiles of concentrations and $\Delta Q T c F$ overlaid with slope of final model and when relevant for key stages during model development may be presented.

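### In the QD schedule the PK sample that may be waived above 50 mg is the 8 h one, which is paired with a triplicate central ECG; moving the waiver to the unpaired 6 h sample would cost nothing

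*Protocol*

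**What the plan says.** Protocol Table 13 sets the PK and ECG times for QD dosing in Part A1, on PK Lead-in Day -3 and on Cycle 1 Day 15. On both days the 6 h row has a PK sample and no ECG. The 8 h row, "8 hours (±45 minutes ^d", has both. Footnote c makes that ECG central and triplicate. Footnote d says "This PK sample is mandatory for Dose Level 1" and then that "PK sampling at this timepoint at subsequent dose levels may be waived by the Sponsor", after PK analysis of Dose Level 1. Dose Level 1 is 50 mg (Section 6.1.1: "The starting dose of TAS3351 will be 50 mg QD"), and the planned levels above it in Table 5 are 100, 200, 350, 500 and 700 mg.

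Table 14 (BID dosing) puts its own waiver footnote on a different row, "6 hours (±35 minutes ^d", which has no ECG. Footnote a of both tables separately lets time points be skipped, on written notice from the Sponsor, when PK evaluation no longer needs them.

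SAP 5.6.7 uses the pairs. Change from baseline in QTcF "versus time-matched plasma concentration will be plotted for PK Lead-in Day -3" (QD) and Day 15, then modelled on concentration with nominal day and nominal time as categorical terms. The listed model checks include "Assumption 3: No time delay between drug concentrations" and change in QTcF.

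**The concern.** The waiver covers the blood draw only. The patient still stays for the 8 h triplicate ECG, which then has no concentration to be matched with. The 6 h draw, whose loss would cost the QTcF analysis no pair, has no waiver of its own.

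QT prolongation is a named risk (Protocol 2.2.1.6: hERG inhibition and a dog telemetry finding), and the exposure-QTcF relationship is a stated exploratory objective of Part A. Part A1 is the only part with central ECGs (Protocol 7.1.2), so later parts cannot replace the lost central pairs. The loss would fall on every dose above the lowest, and on the only matched time between 4 h and 24 h, where a delayed effect could show.

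**Working it through.** **1. Count of matched times (Table 13, rows with both PK and ECG)**

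| Day | All pairs | 8 h PK waived | 6 h PK waived instead |
|---|---|---|---|
| Day -3 | 1, 2, 4, 8, 24, 72 h (6) | 1, 2, 4, 24, 72 h (5) | all 6 kept |
| Cycle 1 Day 15 | pre-dose, 1, 2, 4, 8, 24 h (6) | pre-dose, 1, 2, 4, 24 h (5) | all 6 kept |
| Total per patient | 12 | 10 | 12 |

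The loss is 2/12 = 17% of pairs per patient. Pairs strictly between 4 h and 24 h go from one per day to none, a nominal gap of 24 - 4 = 20 h. The 6 h draw cannot stand in for the 8 h one: its nominal window closes at 6 h 35 min and the 8 h window opens at 7 h 15 min. In Table 14, waiving the 6 h sample loses no pair.

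**2. Effect on the planned model's structure.** Nominal time is categorical in SAP 5.6.7. With the waiver in force, its 8 h level is estimated from 50 mg patients alone.

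**3. Precision if there is no lag (illustration).** Assume 6 patients at each of 6 levels: 6 x 6 x 12 = 432 pairs. The waiver removes 5 x 6 x 2 = 60, leaving 372. The further assumptions are:
- a one-compartment profile, C(t) proportional to dose x [ka/(ka - ke)] x [exp(-ke t) - exp(-ka t)], with half-life 8-24 h and ka 0.25-1 per h;
- a random patient intercept with SD 6 ms and residual SD 8 ms;
- day and categorical time terms.

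The slope's standard error rises by about 3% to 11%. The figure is sensitive to the assumed profile; a repeat calculation gave about 2% to 14%.

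**4. Bias if QTcF lags concentration (illustration).** Assume an effect site with dE/dt = k0 (C - E), k0 = ln 2 / lag half-life, lag half-life 2-4 h, plasma half-life 8-16 h and ka 0.5-1 per h. Generate noise-free effects at all Table 13 pairs on both days and at six doses. Fit concentration, day and categorical time as fixed effects, keeping 8 h at 50 mg in the waived case. Compare slope x Cmax with the true peak effect:

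| | With 8 h pairs | 8 h waived above 50 mg | Change at low / high end |
|---|---|---|---|
| Day -3 | 81-99% | 68-95% | 13 / 4 points |
| Day 15 | 75-89% | 63-86% | 12 / 3 points |

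Even the full schedule understates a lagged effect under this model; the waiver makes the understatement somewhat worse.

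The documents give no human pharmacokinetics or QTcF variances, so every input in steps 3 and 4 other than the doses and sampling times is an assumption. Step 1 needs none.

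**The case against.** The other side has a good deal to say, and much of it stands.

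- The waiver is optional and follows review of Dose Level 1 PK, so the loss is possible, not certain. Ten of 12 pairs remain, and the regression can be fitted.
- The analysis is exploratory, and no dose decision is stated to depend on its slope.
- The delay check in SAP 5.6.7 plots mean concentration and mean change in QTcF over time by dose. It does not require matched pairs. The 8 h QTcF change would still appear at every dose, although with concentrations only at 6 h and 24 h around it. If hysteresis is found, the SAP calls for another model to be explored.
- The 8 h ECGs stay in the central ECG summaries and QTcF categories of SAP 5.6.6.
- The only QTc timing in the documents is the dog finding at 4 h (Protocol 2.1.2.1.1), and the 4 h pair is kept. No passage supports a lag in humans; none excludes it in this first-in-human study.
- The active metabolite is measured and modelled in its own right. That helps, but its 8 h concentration comes from the same waived draw.

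Two stronger readings are tempting. A reader might infer from Table 14 that footnote d in Table 13 is simply misplaced. The documents do not show that: under BID dosing 8 h is the last sample before the second dose and the 24 h row has no ECG, whereas QD dosing has a 24 h pair on both days. A reader might also fit one straight line to a single-dose profile at 1, 2, 4 and 24 h, with and without 8 h, and conclude that the predicted peak effect drops to 33-57% of the truth from 47-76%. That line is not the SAP's model. It leaves out the 72 h pair, all of Day 15, and the day and time terms, and it drops 8 h at 50 mg, where the sample is mandatory.

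**Conclusion.** The point holds as an avoidable weakness in the sampling rule, of modest size. What is certain from the tables is that use of the waiver takes matched pairs from 12 to 10 per QD patient, leaves none between 4 h and 24 h at 100 to 700 mg, and keeps the 8 h ECG without a concentration. What depends on assumption is the consequence: a small loss of precision if there is no lag, and a further understatement of the effect at Cmax of about 3 to 13 points (comparing the ends of the ranges) under an assumed lag half-life of 2 to 4 h. The documents do not support saying that the analysis would fail, that the delay check would be impossible, or that the footnote is a proven error. The case for acting is that the loss would fall on a named safety question that only Part A1 addresses with central ECGs, and that avoiding it is free.

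**What to change.** 1. In Table 13, move footnote d from the 8 h row to the 6 h row on Day -3 and Cycle 1 Day 15. Table 14 already places its waiver there, which makes this a consistent alternative.
2. In footnotes a and d of Tables 13 and 14, state that PK samples at Part A1 central-ECG time points are not waived or skipped on PK grounds alone. Without this, footnote a would still allow the 8 h draw to be dropped.

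The cost is a footnote edit. The same number of samples stays waivable under footnote d, and no draw, ECG or visit is added. Nor is there an obvious loss for the PK profile: keeping 8 h in place of 6 h shortens the last gap before the 24 h sample from 24 - 6 = 18 h to 24 - 8 = 16 h.
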